4.6 Data Collection and Participant Follow-Up

At baseline, we will collect pre-operative demographic and cancer-related data from various sources, including the participant or proxy, the participant's medical chart, and/or the participant's treating surgeon. The data will include details such as age, sex and gender, co-morbidities, life-expectancy based on surgeon estimate and pre-surgical functional status, and anatomic characteristics of the femoral metastatic lesion. Participants will also pre-operatively complete the PROM questionnaires. We will document surgical details, peri-operative care, and in-hospital data, including the timing of surgery and any co-interventions used that may mediate treatment effects (such as post-operative mobilization and therapy), as well as any serious adverse events (SAEs) that occurred during hospitalization. After discharge, participants will be followed for one year, during which they will be assessed by their treating surgeon at two and six weeks; four, six and nine months; and one-year post-surgery. At each visit, we will document physical therapy, ability to ambulate, re-operations, hospitalizations, and SAEs. PROM data will be collected at all visits; however, the burden is low due to the short nature of the questionnaire. The utility score from the PROPr: PROMIS®-Preference Scoring System will be collected at baseline and 6 and 12 months. Trial data will be securely stored in the trial database accessible only to authorized personnel. See **Table 4** below:

Table 4. Study Flow

CATEGORY	STEPS		DATA COLLECTED
Recruitment	Identification of Patients		
	Assessment of Patient Eligibility		Screening Data
	Informed Consent		Informed Consent Form
Pre-Operative (Baseline)	Pre-Operative (Baseline)		Demographics Cancer-related data PROMIS®-PROPr questionnaire PROMIS® Physical Function
	RANDOMIZATION 		
Follow Up Visits	Internal Fixation	Resection and Reconstruction	
	Peri-Operative	Peri-Operative	Surgical details Peri-operative care Serious Adverse Events (SAEs)
	2 Week	2 Week	Follow-Up Data Package: X-rays; PROMIS® Physical Function questionnaire; Demographics, health-related questions, Mortality Status; Patient-reported days at home; Recurrence of cancer; SAEs
	6 Week	6 Week	Follow-Up Data Package: X-rays; PROMIS® Physical Function questionnaire; Demographics, health-related questions, Mortality Status; Patient-reported days at home; Recurrence of cancer; SAEs
	4 Month	4 Month	Follow-Up Data Package: X-rays; PROMIS® Physical Function questionnaire; Demographics, health-related questions, Mortality Status; Patient-reported days at home; Recurrence of cancer; SAEs
	6 Month	6 Month	Follow-Up Data Package: X-rays; PROMIS® Physical Function questionnaire; Demographics, health-related questions, Mortality Status; Patient-reported days at home; Recurrence of cancer; SAEs PROMIS®-PROPr questionnaire
	9 Month	9 Month	Follow-Up Data Package: X-rays; PROMIS® Physical Function questionnaire; Demographics, health-related questions, Mortality Status; Patient-reported days at home; Recurrence of cancer; SAEs
	12 Month	12 Month	Follow-Up Data Package: X-rays; PROMIS® Physical Function questionnaire; Demographics, health-related questions, Mortality Status; Patient-reported days at home; Recurrence of cancer; SAEs PROMIS®-PROPr questionnaire

PROMIS®: Patient-Reported Outcomes Measurement Information System; PROPr: PROMIS®-Preference Scoring System

4.6.1 Maximization of Follow-Up

Post-surgical follow-up is an important element of oncologic care. Therefore, given that our trial follow-up visits align with the standard follow-up practice, we anticipate only minimal losses to follow-up in our MBD population. Nonetheless, the importance of trial compliance both at the beginning of the trial and at each trial visit will be explained to participants. The following procedures will be implemented to minimize losses:

- Any otherwise eligible patient who is likely to present problems with maintaining follow-up will be excluded;
- At the time of randomization, each participant will be asked to provide their contact information, as well as the contact information for their family physician and three alternate contacts;
- If a participant refuses to return for an assessment, they will be asked if they are willing to provide follow-up data via telephone;
- If a participant cannot be reached, their status regarding the primary trial outcome will be assessed by reviewing their medical chart; and
- Trial personnel will remind participants via telephone/email of upcoming clinic visits.

4.7 Protecting Against Sources of Bias

Our pragmatic trial design carefully balances the internal validity of our eventual results and their generalizability to MBD patients beyond our participating clinical sites. We have carefully considered sources of possible bias and safeguards that we might put in place. To ensure internal validity, we will leverage the experience and advanced clinical trial infrastructure of our trial team. These include procedures for maximizing recruitment, maintaining follow-up, ensuring protocol adherence, and the central adjudication of outcomes, which are detailed in the sections below. When possible, we will blind outcomes assessors and data analysts. Bias could intrude through co-intervention, in particular, differential peri-operative management. We will, therefore, mandate a specific peri-operative management protocol (see 4.5.3 Standardization of Perioperative Care). The generalizability of our results is supported by the diversity of our participating hospitals, the screening of all MBD patients, and the surgical procedures used daily for MBD across North America and worldwide.

4.7.1 Data Monitoring

In addition to our strategies to maximize participant retention, we will also implement a Data Monitoring Plan to prevent missing data and protect the integrity of the data quality. Ongoing remote data monitoring will be conducted by our trial team. Specifically, we will monitor the trial database for missing data, inconsistent or implausible data, enrolment rates, the distribution of key data points (e.g., life-expectancy based on surgeon estimate, pre-surgical functional status, and anatomic characteristics of the lesion), follow-up rates, the number and type of outcomes (e.g., lower than anticipated trial events), and protocol deviations reported by each clinical site. Findings from the remote data monitoring will be distributed to the Principal Investigator, as well as to the site investigator and personnel at the respective clinical site. Our trial team will work collaboratively with the clinical site personnel and site investigators to resolve all identified issues, which may necessitate an ad hoc in-person monitoring visit.

If an in-person site monitoring visit is required, items that will be reviewed at each monitoring visit will include: trial master files, trial procedures, screening data and data verification of 20% of the enrolled trial patients, which will be increased if significant issues are identified. Our trial team will also carefully monitor participants' records to ensure that they received the correct interventions. Findings from each monitoring visit will be recorded and distributed to the trial Principal Investigator, as well as to the investigator and personnel at the respective clinical site. Our trial team will work collaboratively with the clinical site personnel and site investigators to resolve all identified issues. Re-training of clinical site personnel will be provided as necessary.

We achieved a 95% follow-up rate in our PARITY trial in which patients with MBD of the femur were included. Since all MBD patients who have undergone surgical management for an impending or realized pathologic fracture require post-surgical follow-up, we anticipate a similar loss to follow-up (LTFU) rate in the PERFORM trial. As in our previous trials, patients will only be withdrawn if they no longer consent to participate or if clinical site personnel are unable to contact them after several attempts for their one-year follow-up visit. Over the course of the trial, clinical site personnel will receive frequent quality control reports generated by the Methods Centre personnel who will summarize missing or overdue data. Our trial team will follow-up regarding these reports, as well as inform the Principal Investigator who may escalate them to the site investigator to develop a plan to submit the overdue data. If necessary, we will conduct in-person monitoring visits to collect any missing or overdue data points.

4.7.2 Adjudication of Outcomes

The use of Central Adjudication Committees (CAC) in randomized controlled trials significantly increases data quality and reduces inaccuracies by minimizing biased outcome assessment and between-site variability. The membership and responsibilities of the PERFORM CAC will be detailed in the PERFORM CAC Charter. Briefly, the PERFORM CAC will be comprised of three orthopaedic oncologists, a medical oncologist and a radiation oncologist. Using pre-defined decision rules that will be documented in the PERFORM CAC Charter, the PERFORM CAC will adjudicate: 1) case eligibility; 2) unplanned re-operations; 3) local recurrence; 4) serious adverse events and 5) mortality (cause of death). The CAC will reach a consensus on all reviewed cases. All decisions made by the Committee will be final. We anticipate that the PERFORM CAC will meet quarterly to review trial events that require adjudication.

4.7.3 Allocation Concealment and Blinding

The participants, local trial personnel and our trial team cannot be blinded to the surgical procedure, given the differences in surgical incisions for the procedures and the surgeon's need to know which procedure to perform. However, the use of random variable block sizes will minimize the risk of selection bias. Given the obvious differences in hardware utilized between the two surgical procedures, it will also be impossible to blind outcomes assessors when adjudicating events that require the review of imaging. However, for events that do not require the review of imaging, outcomes assessors will be blinded. Finally, safety data reported to the PERFORM Data and Safety Monitoring Board (DSMB) will be compiled by a blinded data analyst who is otherwise not involved in the trial to ensure that the PERFORM data analyst remains blinded.

4.7.4 Minimization of Crossovers of Trial Interventions

Unplanned conversions between the two surgical procedures are unlikely, as only patients who are suitable for both surgical procedures will be eligible for the trial. The likelihood of crossovers is further reduced due to the requirement that the surgical equipment for both procedures be available at all participating clinical sites. When possible, local trial personnel will be present in the pre-operative holding area to obtain study consent and during surgery to ensure that the patient undergoes the correct surgical procedure. Nevertheless, any patients who do crossover will be analyzed in the group to which they were originally allocated, maintaining the intention-to-treat approach planned for our analysis.

5.0 Statistical Plan

5.1 Sample Size Determination

The use of hierarchically assessed composite outcomes is becoming more frequent in clinical trials, and it offers several benefits. By utilizing a pre-defined rank, statistical power increases while avoiding concerns of increased type I errors due to multiplicity. This ranked approach also aligns with clinical practice as patients and care providers are typically interested in the treatment effect on multiple outcomes with a defined hierarchy. Detailed simulations were performed to determine the appropriate sample size to adequately power the study. **Table 5** lists the distributional assumptions for each component of the composite outcome by treatment arm. Using 10,000 simulations of these distributions, we determined that 300 patients (150 per group) provided over 90% power to detect superiority with a two-sided alpha of 5% tested with the U-statistic described by Bebu and Lachin²⁶. To account for up to 10% attrition, the trial plans to enroll 334 patients.

Table 5 : Input for sample size estimation.

Rank	Outcome	Resection and Reconstruction	Internal Fixation
1	Death within 12 months	30%	30%
2	Physical function (ability to perform everyday activities) by 4 months		
	Unable to do	5%	10%
	With much difficulty	20%	25%
	With some difficulty	40%	40%
	With little difficult	25%	20%
	Without any difficulty	10%	5%
3	Days at home within 365 days, mean (SD)	340 (20)	300 (20)

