5.2.2 Primary Outcome Analysis

We will hierarchically assess the primary composite outcome using the Win Ratio method. The Win Ratio method is based on the principle that each participant in the clinical trial is compared with every other participant within each stratum in a pairwise manner. All-cause mortality comparisons will be time-to-event and local cancer recurrence will allow for recurrent events using a frailty model. The pairwise comparison proceeds in a hierachal fashion – for example, starting with mortality, followed by physical function, followed by days at home, and finally by local cancer recurrence when participants cannot be differentiated on an outcome of higher importance. If two paired participants both experienced a local cancer recurrence, we will assume a greater frequency of recurrences to be worse. If two paired participants have the same mortality status or frequency of recurrences, we will assume earlier events are worse. For each pairwise comparison, the treatment groups are assigned a

win, loss, or tie. The Win Ratio is the frequency of a favorable outcome in participants assigned to resection and reconstruction divided by the frequency of a favorable outcome in participants assigned to internal fixation with a 95% CI and corresponding p-value calculated using the methods described by Finkelstein and Schoenfeld.

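### The power of over 90% in section 5.1 does not belong to the win rule in section 5.2.2, which gives about 80% at 150 per group

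*Protocol*

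**What the plan says.** Section 5.1 of the protocol bases the sample size on 10,000 simulations from Table 5: "we determined that 300 patients (150 per group) provided over 90% power to detect superiority with a two-sided alpha of 5" per cent, "tested with the U-statistic described by Bebu and Lachin". The 300 are raised to 334 for up to 10% attrition. Table 5 gives 12-month death as 30% in each arm, a five-level function item that favours resection and reconstruction, and days at home with mean 340 against 300 (SD 20). Death enters only as a proportion. No death times are given, and no rule for pairs in which both patients died.

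Section 5.2.2 defines the analysis: "All-cause mortality comparisons will be time-to-event". It adds: "If two paired participants have the same mortality status or frequency of recurrences, we will assume earlier events are worse". A pair moves to the next outcome only if the one above does not separate it. On the set of comparisons it says that "each participant in the clinical trial is compared with every other participant within each stratum in a pairwise manner". The confidence interval and p-value are "calculated using the methods described by Finkelstein and Schoenfeld".

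**The concern.** Death is ranked first, and Table 5 assumes no effect on it. All of the assumed benefit lies in ranks 2 and 3, so power depends heavily on how many pairs get that far. Under 5.2.2 a both-dead pair stops at rank 1, decided by who died first. If death is instead a yes/no item, the same pair is tied at rank 1 and could be passed down to outcomes on which resection and reconstruction is assumed to do better. The two rules cannot give the same power, and section 5.1 does not say which one was simulated.

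The enrolment target of 334 rests on this one power figure. If the figure belongs to a different rule, the trial's real risk of a false negative is understated to everyone who relies on it.

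**Working it through.** **Inputs (Table 5).** Death 30% in both arms. Function, worst to best: 5, 20, 40, 25, 10% for resection and reconstruction; 10, 25, 40, 20, 5% for internal fixation. Days at home: 340 (20) and 300 (20). Two-sided 5%, 150 per group. My assumptions: independent components, normal days at home, the same death-time distribution in both arms, no stratification.

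**Step 1, a pair that reaches function.**
- Function win: 0.20×0.10 + 0.40×0.35 + 0.25×0.75 + 0.10×0.95 = 0.4425
- Function tie: 0.005 + 0.05 + 0.16 + 0.05 + 0.005 = 0.27; loss 0.2875
- Days-at-home win: Φ(40/√(20²+20²)) = Φ(40/28.28) = 0.921
- Overall win: 0.4425 + 0.27×0.921 = 0.691; loss 0.309

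**Step 2, pair types.** Both alive 0.7² = 0.49; exactly one dead 2×0.3×0.7 = 0.42 (0.21 each way); both dead 0.3² = 0.09.

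**Step 3, three ways to treat both-dead pairs.**
- Passed down: W = 0.21 + 0.58×0.691 = 0.611
- Left tied: W = 0.21 + 0.49×0.691 = 0.549, L = 0.21 + 0.49×0.309 = 0.361
- Decided on time of death (5.2.2): W = 0.21 + 0.045 + 0.49×0.691 = 0.594

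| Both-dead pairs | W | L | Win ratio | Simulated power, Bebu-Lachin |
|---|---|---|---|---|
| Passed down | 0.611 | 0.389 | 1.570 | 91.2% (10,000 runs) |
| Left tied | 0.549 | 0.361 | 1.519 | 80.6% (10,000 runs) |
| Time of death (5.2.2) | 0.594 | 0.406 | 1.461 | 79.6% (20,000 runs, Monte Carlo SE 0.3 points) |

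The first row reproduces the protocol's figure; the row that follows 5.2.2 does not. Repeat simulations with separate code gave 90.7% to 91.6% for the first row and 79.1% to 80.0% for the last. Simulated type I error was 0.050.

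**Step 4, hand check.** With continuous days at home, the first and last rules each rank all patients without ties, so the score test is close to a Mann-Whitney test. Its null standard error for W is √((2n+1)/(12n²)) = √(301/270,000) = 0.0334.
- Rule of 5.2.2: (0.5937 − 0.5)/0.0334 = 2.81; power Φ(2.81 − 1.96) ≈ 80%
- Passed down: (0.6109 − 0.5)/0.0334 = 3.32; power Φ(3.32 − 1.96) ≈ 91%

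**Step 5, whether something else closes the gap under the rule of 5.2.2.**
- Finkelstein-Schoenfeld test in place of Bebu-Lachin: 81.3%
- Exponential in place of uniform death times: 79.8%
- Days at home capped at 365: 79.5%
- Correlation of function with days at home (assumed, on a latent normal scale): 0.5 gives 79.6%, 0.8 gives 84.3%, 0.95 gives 87%
- All 334 analysed (167 per group): 83.1%
- Local recurrence, the fourth level in 5.2.2, is not in Table 5; continuous days at home leaves almost no ties for it to break

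**Step 6, size for 90% under the rule of 5.2.2.** 200, 205 and 210 per group give 89.1%, 90.2% and 90.9% (4,000 runs each). About 205 per group is 410 evaluable; 410/0.9 = 455.6, so 456 enrolled.

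**The case against.** The best defence is that the figure is no arithmetic slip. With death as a yes/no item, as Table 5 has it, and both-dead pairs passed down, it reproduces. The Study Summary and sections 1.7 and 3.2.1 describe rank 1 as mortality at or within 12 months, which fits a proportion. Section 5.2.2 also carries a recurrence level found in neither Table 2 nor Table 5, so it may be the text that needs correcting. This stands in part: the fault could lie in either section, and the view that the sponsor's simulation passed both-dead pairs down is an inference from the match. But 5.2.2 is the stated primary analysis, and the quoted power is not its power, whatever was simulated.

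A second defence is that Table 5 fixes the proportion dying, not the times. If the resection patient died later in about 67% of both-dead pairs, the rule of 5.2.2 would give 90.7%. If that share were about 41%, power would be 70.4%. The protocol assumes neither, and section 1.2 says surgery is unlikely to lengthen life. A common death-time distribution is the natural reading, but it is an assumption and should be stated.

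Finally, about 80% power is a usual level and type I error is unaffected. That is true. It limits the harm but does not make the stated figure correct.

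**Conclusion.** The concern holds. On the protocol's own inputs, the primary analysis as written has about 80% power at 150 per group (win ratio about 1.46), not over 90%. The chance of missing the assumed effect is about one in five. The base case assumes independent components and equal death-time distributions. Neither the choice between the two named tests, nor a correlation up to 0.95 between function and days at home, nor full retention of all 334 brings power to 90%. The validity of the primary test is not in question.

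Stratification is outside this conclusion. If the strata in 5.2.2 are the randomization strata, power could be lower still: for 20 to 30 equal-sized sites, a 50:50 fracture split and no site effect, 71% to 66% unweighted or 75% to 69% with inverse-size weights (1,500 runs each). Those figures rest on assumptions the protocol does not give, and the loss could shrink or reverse if sites differ.

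**What to change.** Re-run the simulation with the exact pairwise rule of 5.2.2 and replace the power statement in 5.1 with the result. Possible wording: *With death compared on time to event (earlier death worse), the same death-time distribution in both arms and independent components, 300 evaluable patients (150 per group) give about 80% power for a win ratio of about 1.46.* State the both-dead rule and the assumed correlation in 5.1, and include the strata and their weights in the re-run if the analysis is stratified by the randomization factors.

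The sponsor then chooses: accept about 80%, enlarge the trial (about 456 enrolled for 90%), or change the both-dead rule. A change of rule must be made in 5.1 and 5.2.2 together, before anyone sees outcomes by arm. Correcting the statement alone costs one re-run of existing code, a short edit to 5.1 and a less favourable stated power. Enrolment and conduct need not change.

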5.2 Statistical Methods

5.2.1 Analysis Plan Overview

While conducting the analyses, the data analysts will remain blinded to treatment allocation. The analysis and reporting of the trial will follow the CONSORT criteria (www.consort-statement.org). The process of participant enrolment and flow through the study will be summarized using a flow diagram. Participant demographics and baseline outcome variables will be summarized using descriptive statistics reported as mean (standard deviation) or median (interquartile range) for continuous variables depending on the distribution, and count (percent) for categorical variables. All analyses will use the intention-to-treat principle. We do not plan to conduct a formal interim analysis for efficacy, as the trial will not be stopped early for benefit due to the risk of overestimating treatment effects. Secondary analyses will be exploratory with no adjustments for multiple comparisons.

5.2.2 Primary Outcome Analysis

We will hierarchically assess the primary composite outcome using the Win Ratio method. The Win Ratio method is based on the principle that each participant in the clinical trial is compared with every other participant within each stratum in a pairwise manner. All-cause mortality comparisons will be time-to-event and local cancer recurrence will allow for recurrent events using a frailty model. The pairwise comparison proceeds in a hierachal fashion – for example, starting with mortality, followed by physical function, followed by days at home, and finally by local cancer recurrence when participants cannot be differentiated on an outcome of higher importance. If two paired participants both experienced a local cancer recurrence, we will assume a greater frequency of recurrences to be worse. If two paired participants have the same mortality status or frequency of recurrences, we will assume earlier events are worse. For each pairwise comparison, the treatment groups are assigned a

win, loss, or tie. The Win Ratio is the frequency of a favorable outcome in participants assigned to resection and reconstruction divided by the frequency of a favorable outcome in participants assigned to internal fixation with a 95% CI and corresponding p-value calculated using the methods described by Finkelstein and Schoenfeld.

